#### **B3. DESCRIPTION OF RESEARCH PROTOCOL**

A. Study Design – Overview, Methods, Procedures

- We will identify patients with AP based on the 2012 revised Atlanta criteria for diagnosis,
   i.e., AP is diagnosed if 2 out of the following 3 criteria are met:
- Acute onset of persistent, severe, epigastric pain often radiating to the back,
- Elevation in serum lipase or amylase to three times or greater than the upper limit of normal,
- Characteristic findings of acute pancreatitis on imaging (contrast-enhanced computed tomography [CT], magnetic resonance imaging [MRI], or transabdominal ultrasonography).
- Patients will be recruited for participation in this study while they are hospitalized with AP at Beth Israel Deaconess Medical Center. Once the patient has been transferred from the ED to the hospital floor, we will identify and recruit them for participation in our study.
- After obtaining informed consent from the patient, the patient will be enrolled by simple randomization to either the PCA or the PDA arm of the study. The research staff will assign patients to either the PCA arm or the PDA arm based on a standard randomization. Once, a patient has consented, the research staff will assign them to the next sequential study ID and corresponding study arm and let the attending hospitalist know of the result. The patient will then be enrolled in their assigned arm.
- The initial protocol for analgesic administration in each arm is as follows:

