after transition to PO opioids. The modality of IV opioid administration will revert to the assigned treatment arm.

- Other aspects of each patient's routine clinical care will continue as per the attending physician under whom the patient is admitted regardless of treatment arm status (PDA vs PCA).
- At the end of their hospital stay, we will document the following outcomes:
  - 1. Primary outcome: Length of stay (days)
  - 2. Secondary outcomes:
  - a. Number of hours the patient is NPO before diet is initiated
  - b. Mean pain scores on NRS over the first 24 hours, second 24 hours and course of their hospital stay
  - c. Total opioid dose for pain control during hospitalization (average MME during hospital stay)
  - d. Time to transition to PO opioids
  - e. Opioid-related adverse events/side effects: respiratory decompensation, sleep-disordered breathing, hypotension, nausea, vomiting, constipation, drowsiness, confusion, delirium or other mental status changes, myoclonus, headache, urinary retention, physician suspected opioid abuse or any form of allergic reaction.
  - f. Use of naloxone and antiemetics
  - g. Number of rescue doses required daily and in total through the hospital stay
  - h. ICU transfer
  - i. 30-day readmission rates
  - j. All-cause inpatient mortality and opioid-related inpatient mortality
  - k. 30-day mortality
  - I. Daily MME on discharge
- We expect to enroll patients over a 36-month period from the start date of the study. Based on this, we expect patient enrollment to end by 4/30/2024. We will plan to perform data analysis at two points: 1. Interim data analysis at a predetermined point in the study (mid-point of study), and 2. At the end of the study once patient enrollment has been completed.

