# C. Subject Selection

We will study 174 patients admitted within 24 hours to the hospital with AP between 18 and 65 years of age. Patients will be randomized to receive IV opioids either via PCA (n=87) or PDA (n=87). Exclusion criteria are as follows: known allergy or contraindication to opioids, active illicit drug use, chronic pancreatitis, pancreatic cancer, acute encephalopathy/psychiatric illness that would preclude ability to use PCA, chronic renal insufficiency with a Cr >2, acute renal insufficiency with a Cr >3, and known allergy to acetaminophen or hepatic dysfunction otherwise limiting acteaminophen use.

Inclusion criteria	Exclusion criteria
Diagnosis of AP confirmed by revised Atlanta criteria	Active illicit drug use
	Discharged from the ED
Admitted to the medical floor within 48 hours of ED arrival	Direct admission to ICU from ED
	Known allergy to opioid medications
Age 18-65	Age <18 or >65
	Known chronic pain syndrome or concurrent medical condition with chronic pain
	Active
	encephalopathy/confusion/delirium/psychiatric

Study Description – Part B CCI Form: 9-2015 PI Revision Date: 3/2/2021

illness or any other condition that limits capacity
Known chronic opioid use
Renal insufficiency (baseline Creatinine of >2 and/or AKI with Cr>3 on admission)
Known allergy to acetaminophen or hepatic dysfunction otherwise limiting acetaminophen use

Subjects will be enrolled without regard to race, gender, or vulnerable category status.

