## **B6. RECRUITMENT AND CONSENT PROCEDURES**

## Recruitment

Patients will be identified as they are admitted to the hospital for management of AP. Our research staff will check with the admitting hospitalists/physicians on a daily basis for patients admitted with AP who may be eligible for enrollment in the study. Once we have identified a patient who meets the study criteria, our research staff will approach the patient and obtain informed consent.

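### No secondary outcome is timed from randomisation, so whole-stay pain and opioid dose include time before assignment, and the 24-hour pain windows, NPO hours and time to oral opioids have no stated start

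*Combined protocol and SAP*

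**What the plan says.** The outcome list closing Section B3.A defines the relevant secondary outcomes as follows:

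- (a) "Number of hours the patient is NPO before diet is initiated": no start time given.
- (b) "Mean pain scores on NRS over the first 24 hours, second 24 hours and course of their hospital stay": the third window is the hospital stay; the first two have no stated origin.
- (c) "Total opioid dose for pain control during hospitalization (average MME during hospital stay": the frame is the hospitalisation.
- (d) "Time to transition to PO opioids": no start time given.

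The primary outcome, length of stay in days, also has no stated start.

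Assignment happens some way into the stay. Section B3.A says: "Once the patient has been transferred from the ED to the hospital floor, we will identify and recruit them for participation in our study". Randomisation then follows informed consent. Under Section B6, Recruitment: "Our research staff will check with the admitting hospitalists/physicians on a daily basis for patients admitted with AP".

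Section B3.C limits the time to admission but not the time to randomisation, and it gives two limits. The text speaks of patients admitted within 24 hours, while the table has "Admitted to the medical floor within 48 hours of ED arrival".

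The Data Analysis paragraph in Section B3.B sets no time zero and no adjustment for baseline pain or opioid use.

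**The concern.** Care given before assignment cannot differ between arms except by chance. If those hours are averaged into a pain score, the difference between arms shrinks in proportion to their share of the window. If pre-assignment doses are added into an opioid total, they add variance and no information about the arm. If a diet was started before randomisation, outcome (a) is already settled for that patient.

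The background section says that adequate pain control often needs IV opioids in the first 24 to 48 hours. Doses before assignment are therefore likely, and the hours at issue are among those when pain treatment is most intensive. A real difference in early pain could be reported as little or no difference.

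Where the start is unstated, an analyst could also choose between an admission clock and a randomisation clock after seeing the data.

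**Working it through.** **The plan's own figure.** The sample size is for length of stay: d = 0.42, 5% error, 80% power, 87 per group (Section B3.B). The two-sided normal approximation gives n = 2 × (1.960 + 0.842)² / 0.42² = 89 per group, close to the stated 87. At 87 per group the power is 79%. The timing of the secondary outcomes does not affect this figure.

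**Which outcomes include pre-assignment time by their wording.** Opioid dose (c) and the third pain window in (b) are framed by the hospital stay, and every patient has ED and some floor time before randomisation. These two therefore include it. The first two pain windows, (a) and (d) include it only if counted from arrival or admission, which the text neither states nor rules out.

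**First-24-hour pain window, if counted from admission.** Let r be the hours from the start of the window to randomisation. If the effect is immediate and constant and scores are evenly spaced, the share of the effect kept is (24 − r)/24. The documents give neither r nor a target difference for pain. The table therefore assumes a true difference of 1.5 NRS points and, separately, a standardised effect of 0.42 with unchanged SD. The 0.42 is borrowed from length of stay for illustration only.

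| r (h) | Share kept | 1.5 points appears as | Effect 0.42 becomes | Power, 87 per arm | n per arm for 80% |
|---|---|---|---|---|---|
| 0 | 100% | 1.5 | 0.42 | 79% | 89 |
| 4 | 83% | 1.25 | 0.35 | 64% | 129 |
| 6 | 75% | 1.125 | 0.315 | 55% | 159 |
| 12 | 50% | 0.75 | 0.21 | 28% | 356 |
| 24 | 0% | 0 | 0 | nothing to detect | – |

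At r = 36 the first window holds no assigned treatment, and (48 − 36)/24 = 50% of the second window remains.

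**Whole-stay mean pain.** The diluted share is r/(24 × stay in days). With the 6.4-day mean stay of the retrospective IV-push group:

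- r = 12: 12/153.6 = 8%, and required n is multiplied by 1/(1 − 0.078)² = 1.18
- r = 24: 24/153.6 = 16%, factor 1.41
- r = 48: 48/153.6 = 31%, factor 2.12

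**Opioid dose.** Item (c) calls itself both a total and an average. As a total, earlier doses add the same expected amount to each arm, so the expected difference is intact and only the variance grows. As an average over the stay, the difference is also diluted.

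**Length of stay.** Time before randomisation is additive. The equal-weight pooled SD of the retrospective figures is √[(7.14² + 9.86²)/2] = 8.61 days, so d = 3.5/8.61 = 0.407. Adding independent pre-randomisation time with an SD of 24 hours (assumed) gives an SD of √(8.61² + 1²) = 8.67 and d = 0.404. The change is negligible.

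**The case against.** The strongest reply is that an undefined start is not the same as a start at admission. In (b), the words about the hospital stay may qualify only the third window. Section B3.A introduces the 4-hourly NRS as the means of judging how well each arm controls pain, which fits a clock starting with assigned treatment. That stands for the two 24-hour windows, (a) and (d), where the fault is a missing definition. It does not reach opioid dose or whole-stay pain, whose frame is written down.

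The delay may also be short. Section B6 says patients are identified as they are admitted, and the 24-hour wording in Section B3.C could be read as a limit that removes the longer delays. If the window starts at floor admission, the 48-hour allowance from ED arrival adds nothing to r. All of this stands, and it is why the figures are shown over a range.

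A reader might infer that the whole first 24 hours is normally spent before assignment. The documents permit that in the extreme but give no distribution of delay, so they do not support it as the usual case. A reader might also take Section B4 to single out early pain as the main expected benefit. It speaks only of better pain control that may lead to earlier oral transition and shorter stays.

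**Conclusion.** The point holds as a gap in the definition of secondary outcomes. Whole-stay mean pain and total opioid dose include time before assignment as written. The 24-hour pain windows, NPO hours and time to oral opioids have no stated start and could be counted to include it.

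The consequence is dilution of mean pain differences and added noise in opioid dose. For the first 24 hours, 75%, 50% or 0% of the effect remains at delays of 6, 12 or 24 hours. This assumes a clock from admission, an immediate and constant effect, and evenly spaced scores. Whole-stay pain loses less: 8% at 12 hours and 16% at 24 hours on a 6.4-day stay. The actual delay is unknown.

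Two stronger readings are not supported. One is that the comparison is biased: randomisation balances pre-assignment hours between arms on average. The other is that the primary outcome must be redefined: d moves only from 0.407 to 0.404, and a change would move it away from the length-of-stay data behind the sample size.

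**What to change.** In the outcome list of Section B3.A, set time zero at randomisation for the following:

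- Pain: mean NRS at 0–24 hours, at 24–48 hours, and from randomisation to discharge.
- Opioid dose: MME from randomisation.
- Oral transition: time from randomisation to PO opioids.
- NPO: hours from randomisation, with a stated rule for analysing patients already on a diet at that point.

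Record the time of randomisation, and treat NRS scores and MME before it as baseline values. Reconcile the 24-hour and 48-hour admission wording in Section B3.C.

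Leave the primary outcome as total length of stay; stay from randomisation can be a sensitivity analysis.

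The cost is a wording change and one recorded time. Sample size and clinical care are unaffected. Opioid totals become less comparable with published whole-stay figures, but those can still be reported descriptively.

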# Recommended for all patients:

PO Acetaminophen 1000 mg Q8H scheduled

- IV Naloxone 40-80 mcg PRN for respiratory depression (RR<10) or significant somnolence
- PO Benadryl 25mg Q4H PRN moderate to severe pruritis
- Recommended algorithm for transition to oral:
- PO Oxycodone 5mg Q4H PRN for pain 4-6
- PO Oxycodone 10mg Q4H PRN for pain 7-10
- Rescue PO Oxycodone 5mg Q2H PRN for pain 4-10 = only to be given as a 'rescue dose' if patient has persistent pain despite using Q4H PO oxycodone (breakthrough pain)
- Dosing and frequencies of medications in the above algorithms are recommendations. The recommended doses are not required for maintenance in the study and we anticipate that they may change given patient characteristics and variable response to medication, the rapidly evolving nature of acute pancreatitis, and hospitalist preferences. However, the mode of IV opioid administration (PDA vs PCA) should remain as assigned until transition to PO opioid.
- Each patient will be closely monitored for adverse events related to opioid
  administration to include cardiorespiratory decompensation, hemodynamic
  instability, nausea, vomiting, confusion, altered mental status, headache,
  drowsiness, etc. This monitoring will include continuous pulse oximetry in addition to
  vital sign measurement every 4 hours.
- The efficacy of each treatment arm to adequately control the patient's pain will be assessed with scheduled use of the Numeric Rating Scale (NRS) every 4 hours by the nursing staff. Pain rating on the NRS will be documented by the nursing staff after each assessment. In an NRS, patients are asked to circle the number between 0 and 10 that fits best to their pain intensity. Zero usually represents 'no pain at all' whereas 10 represents 'the worst pain ever possible'.
- Likert scale of 1 to 10 (1 = Very poor, 10= excellent) will be used to grade overall patient satisfaction with pain control.
- Once each patient's pain is well controlled on IV opioid administration (as determined by the attending physician) and they can tolerate intake by mouth, transition from IV to PO opioid medication can be made in each arm by the attending physician. If the patient is unable to tolerate either the PDA or the PCA arm for any reason and requires switching over to the other arm as part of his/her clinical care, they will be withdrawn from the study and their data will be excluded while analyzing the results. AP has a variable course and may require IV opioids

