#### B. Statistical Considerations

# a. Sample Size Justification:

- Data from a retrospective study of acute pancreatitis patients receiving either patient-controlled analgesia (PCA, n=116) or conventional IV push (IVP, n=647) showed that mean length of stay was higher in the PCA group (9.9 ± 7.14 days) compared to the IVP group (6.4 ± 9.86 days). The effect size calculated using this data yielded a Cohen's d=0.42. Therefore, assuming a 5% error probability for two groups, the estimated sample size to achieve 80% statistical power was determined to be 87 patients per group. At the midpoint of the study when half of target sample size is reached, preliminary post-hoc analysis will be performed to determine effect size and statistical power.

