#### **B4. POSSIBLE BENEFITS**

Patients in this study will obtain no direct benefits from participation in the study. We hypothesize that based on prior studies in postsurgical patients, patients in the PCA arm may potentially have better control of their AP-related pain as compared to conventional physician directed analgesia. This may potentially result in higher patient satisfaction, early transition to oral analgesics, and shorter hospital stays. This information will be helpful in better management of the patients' pain with a PCA protocol in the future.

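### Whole-stay mean NRS is averaged over a window set by the primary outcome; if pain falls and stay differs by arm, the comparison is distorted against the shorter-stay arm

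*Combined protocol and SAP*

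**What the plan says.** The outcome list in section B3.A makes length of stay in days the primary outcome. Secondary outcome b is "Mean pain scores on NRS over the first 24 hours, second 24 hours and course of their hospital stay". Pain is measured by "scheduled use of the Numeric Rating Scale (NRS) every 4 hours by the nursing staff", so each patient contributes about six scores a day until discharge.

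The Data Analysis section (B3.B.b) compares outcomes by a t-test or a Mann-Whitney test. It has no adjustment for stay, no longitudinal model of the scores, no ranking of the three pain windows, and no rule for patients who leave before 48 hours. The start of the first 24 hours (admission or randomisation) is not defined.

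The plan expects stay to differ between arms, but its sources point in opposite directions. Section B4 says of better pain control with PCA: "This may potentially result in higher patient satisfaction, early transition to oral analgesics, and shorter hospital stays". The Sample Size Justification (B3.B.a) uses retrospective data in which "mean length of stay was higher in the PCA group (9.9 ± 7.14 days) compared to the IVP group (6.4 ± 9.86 days".

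No NRS trajectory is given. Improvement is implied: B2 places the need for IV opioids mainly in the first one to two days, and B3.A allows the move to oral opioids once pain is controlled. B3.A also warns that the course is variable and that IV opioids may be needed again.

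**The concern.** A mean over the whole stay has a denominator that is determined after randomisation and that treatment may change. If pain declines with recovery, each extra day in hospital adds low scores and pulls the patient's mean down, while a short stay leaves the mean dominated by the high early scores. Two arms with the same pain hour by hour would then differ on this summary only because their stays differ.

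If PCA shortens stay, as B4 hopes, its whole-stay mean is pushed up, and the trial could report a shorter stay with apparently worse pain. If PCA lengthens stay, as in the retrospective data, it could appear to control pain better. The distortion arises in the situation the trial is built to detect, a difference in stay. With three unranked windows, nothing stops the whole-stay result from being read as the pain finding.

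**Working it through.** **The plan's own figure.** The plan states no expected value or difference for NRS. Its only sample-size calculation is for stay: "The effect size calculated using this data yielded a Cohen's d=0.42" and 87 per group. With two-sided alpha 0.05 (sidedness is not stated) and 80% power, n = 2 × (1.960 + 0.842)² / 0.42² = 89 per group, within 2 of the stated 87. That calculation does not involve the pain outcome.

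**Inputs.** Stays of 6.4 and 9.9 days (B3.B.a); scoring every 4 hours (B3.A); 87 per arm. At six scores a day, a 3.5-day difference in stay adds 3.5 × 6 = 21 scores, all late. The pain curve is an assumption.

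**Step 1: identical decay in both arms.** With NRS(t) = 8·exp(−t/τ), the mean over a stay of L days is 8·τ·(1 − exp(−L/τ)) / L.

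| τ (days) | L = 5.4 | L = 6.4 | L = 9.9 | 6.4 vs 9.9 | 5.4 vs 6.4 |
|---|---|---|---|---|---|
| 1 | 1.47 | 1.25 | 0.81 | 0.44 | 0.23 |
| 2 | 2.76 | 2.40 | 1.60 | 0.79 | 0.37 |
| 3 | 3.71 | 3.31 | 2.33 | 0.97 | 0.40 |

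For τ = 2 and L = 6.4: 16 × (1 − 0.041) / 6.4 = 2.40. Differences are taken before rounding. The shorter stay always has the higher mean.

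**Step 2: other curves, 4-hourly scores, 6.4 vs 9.9 days.**

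| Assumed curve | 6.4 days | 9.9 days | Difference |
|---|---|---|---|
| From 8, half-life 1 day | 1.86 | 1.22 | +0.64 |
| From 8, half-life 2 days | 3.27 | 2.30 | +0.97 |
| From 8, half-life 3 days | 4.22 | 3.18 | +1.04 |
| From 8 towards 2, half-life 1 day | 3.39 | 2.92 | +0.48 |
| From 8 towards 2, half-life 2 days | 4.45 | 3.73 | +0.73 |
| Linear, 8 to 1 at 1 point a day | 4.83 | 3.51 | +1.32 |
| Flat at 5 | 5.00 | 5.00 | 0 |
| Rising from 4 by 0.2 a day | 4.63 | 4.98 | −0.35 |

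The sign depends on the direction of the curve.

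**Step 3: variable stays.** This simulation used 87 per arm, 300 replicates per scenario, lognormal stays, the same distribution of declining pain curves in both arms (half-life 1 to 3 days, end level 0 or 2), and a t-test on patient means.

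- Mean stay 6.4 vs 9.9 days (SDs as in the plan, or 5 in both arms): the whole-stay mean was 0.75 to 1.51 points higher in the shorter-stay arm and was declared different in 99–100% of replicates.
- Same patients, 0–24 h mean: difference −0.02 to +0.02, rejection 2–8%, consistent with 5%.
- Same stay distribution in both arms (mean 6.4, SD 5): whole-stay rejection 3–6%.

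**Step 4: discharge linked to pain.** Suppose, for illustration only, that patients leave when NRS has fallen from 8 to 2, and one arm truly improves faster (half-life 1.5 vs 2.5 days). Stays are 3.0 and 5.0 days. The 48-hour means on 4-hourly scores are 5.42 vs 6.28, a clear benefit. The whole-stay means are 4.50 vs 4.43. The reason is algebraic: an exponential fall from 8 to 2 averages (8 − 2) / ln(8/2) = 4.33 whatever its speed, and the 4-hourly grid explains the small departures. The benefit disappears from the whole-stay summary.

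**The case against.** The strongest defence is that the same sentence already contains the remedy. The first and second 24-hour means are fixed windows. The first is not affected in this way, and the second only through discharge before 48 hours. A reader who saw an odd whole-stay result would have both beside it. This stands and limits the point: it concerns one of three windows in one of twelve secondary outcomes (a to l).

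The size is also open to challenge. Step 1 keeps pain identical while stay differs by 3.5 days, a gap from a retrospective comparison. With τ = 2 days, NRS falls below 1 at 2 × ln 8 = 4.2 days, so the patient staying 9.9 days spends 5.7 of them almost free of pain. When discharge follows pain relief (step 4), the gap is only 0.07 points. This stands too: 0.8 points is not a prediction. But step 4 does not clear the summary, because a real benefit is then hidden.

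A reader might infer that the arm leaving sooner must look more painful. The documents do not support that: it needs both falling pain and a difference in stay, and they give no trajectory and note a variable course. Nor do they support calling the whole-stay mean a main efficacy measure. Stay is the sole primary outcome, and no section ranks this window above the other two.

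Finally, a 0–48 h mean adds little to the two planned windows, and dropping the whole-stay comparison loses late and relapsing pain. Both are fair and are reflected in the fix.

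**Conclusion.** The point holds conditionally. The whole-stay window is set by the primary outcome, and the planned tests do not allow for it. If pain falls during the stay and stay differs by arm, the comparison is distorted against the shorter-stay arm, or masks a true faster improvement.

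Under the assumed exponential decay, the spurious gap is 0.4 to 1.0 points at the plan's two mean stays and 0.2 to 0.4 points for a one-day difference; other declining shapes and variable stays gave up to about 1.5. It is zero with flat pain or with the same stay in both arms, and reversed with rising pain. These figures illustrate the mechanism and do not estimate the bias in this trial.

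The primary analysis, the sample size and the first 24-hour mean are unaffected. The change should still be made: it is cheap, and section B3.A names NRS as the means of judging pain control in each arm.

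**What to change.** In B3.A and B3.B.b:

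1. Make the fixed-window NRS means the formal between-arm pain comparison, counted from randomisation: 0–24 h and 24–48 h, or one combined 0–48 h time-weighted mean from the scheduled 4-hourly scores.
2. State a rule for patients discharged before 48 hours, since truncation returns there, and report how many there are in each arm.
3. Report the whole-stay mean as descriptive only, beside length of stay, with no test.
4. If late pain matters to the investigators, add a longitudinal model of NRS over a common period, and state what it assumes about scores missing after discharge.

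The cost of items 1 to 3 is a change of wording and, if the combined window is chosen, one derived variable from scores already charted. No new patients or assessments are needed. The downside is that late and relapsing pain leaves the formal comparison unless item 4 is adopted, and item 4 costs some analysis effort and a missing-data assumption.

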# b. Data Analysis:

- Primary and secondary outcomes of interest will be studied as outlined above. Data will be presented as mean ± standard deviation, median [interquartile range; range], and count (percentage), as appropriate. Data will be graphed, QQ plots performed and Shapiro-Wilk test utilized to assess for normality. Statistical tests for primary and secondary outcome will be compared using independent samples t-test and Mann-Whitney U test, as appropriate. Categorical variables were investigated using Pearson's Chi-Square. Statistical significance will be assigned at 0.05. All data will be analyzed using the R statistical software.

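### Mean NRS pain scores are compared without the pain score before randomisation as a covariate, which gives up precision on a secondary outcome that could be had at almost no cost

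*Combined protocol and SAP*

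**What the plan says.** Secondary outcome (b), in the outcome list of section B3.A, is "Mean pain scores on NRS over the first 24 hours, second 24 hours and course of their hospital stay". For the first of these, "Mean pain scores on NRS over the first 24 hours", the section does not say when the 24 hours begins.

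Under the recommendations for all patients, each arm's control of pain is assessed by "scheduled use of the Numeric Rating Scale (NRS) every 4 hours by the nursing staff", and "Pain rating on the NRS will be documented by the nursing staff after each assessment".

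Section B3.B.b (Data Analysis) states: "Statistical tests for primary and secondary outcome will be compared using independent samples t-test and Mann-Whitney U test, as appropriate". It adds: "Statistical significance will be assigned at 0.05". Neither section names a baseline pain score, a covariate, an analysis of change from baseline or a repeated-measures model.

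On allocation, section B3.A says that "the patient will be enrolled by simple randomization to either the PCA or the PDA arm of the study". No stratification by pain is described.

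**The concern.** Mean NRS is a secondary outcome, but it carries much of the trial's rationale. Section B3.A uses the NRS to assess how well each arm controls pain. Section B4 hypothesises better pain control with PCA and suggests that satisfaction, earlier oral transition and shorter stay may follow from it. The sample size in section B3.B.a rests on length of stay alone, so the pain comparison has no power calculation of its own.

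A patient's pain before allocation may well predict pain over the following day. Patients are recruited after transfer to the floor, and the eligibility table allows floor admission up to 48 hours after ED arrival, so they may enter at different stages of illness and treatment. If starting pain does predict later pain, a two-sample test leaves that explained variation in the error term, and the interval for the arm difference is wider than it needs to be. At stake is the width of that interval.

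**Working it through.** **Inputs from the documents.** 87 patients per arm (B3.B.a and B3.C); significance level 0.05 (B3.B.b), taken as two-sided because sidedness is not stated; NRS every 4 hours (B3.A), so 24/4 = 6 scores per 24-hour window.

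**Input not in the documents.** The correlation r between the score before randomisation and the later mean NRS. It is assumed to be 0.3 to 0.7.

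**1. The plan's own figure.** With d = 0.42, 80% power and two-sided 5%, n per group = 2(1.960 + 0.842)²/0.42² = 89 (90 by the t distribution), close to the stated 87. That figure concerns length of stay. The plan states none for pain.

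**2. Unadjusted pain comparison.** SE = SD × √(2/87) = 0.152 SD. The difference detectable with 80% power is 0.427 SD by the t distribution, or 0.425 SD by the normal approximation.

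**3. Adjusted comparison.** With baseline NRS in a linear model, residual variance is multiplied by 1 − r², and the SE and detectable difference by √(1 − r²). The unadjusted analysis would need 87/(1 − r²) per arm to match.

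| Assumed r | Variance cut (r²) | SE multiplier | SE (SD) | Detectable difference (SD) | Equivalent n per arm |
|---|---|---|---|---|---|
| 0 | 0% | 1.000 | 0.152 | 0.427 | 87 |
| 0.3 | 9% | 0.954 | 0.145 | 0.407 | 96 |
| 0.5 | 25% | 0.866 | 0.131 | 0.370 | 116 |
| 0.7 | 49% | 0.714 | 0.108 | 0.305 | 171 |

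A simulation of 10,000 trials at each r gave SE multipliers of 0.958, 0.868 and 0.720. Estimating the slope therefore costs almost nothing.

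**4. The two windows separately.** Take one baseline score, then scores 1 to 6 (first 24 h) and 7 to 12 (second 24 h). The correlation of baseline with a window mean is the mean of the six baseline-to-score correlations divided by the SD of the window mean, with each single score given SD 1.

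- *Equal correlation c between any two scores.* r = c/√((1 + 5c)/6). For c = 0.3, r = 0.3/√0.417 = 0.465 and variance falls 22%. For c = 0.5, r = 0.5/√0.583 = 0.655 and variance falls 43%. Both windows gain equally.
- *Correlation that decays with time (AR(1)).* The gain then differs sharply by window:

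| Correlation per 4 h | First 24 h: r, variance cut | Second 24 h: r, variance cut |
|---|---|---|
| 0.7 | 0.457, 21% | 0.054, 0.3% |
| 0.8 | 0.596, 36% | 0.156, 2.4% |
| 0.9 | 0.774, 60% | 0.412, 17% |

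Under decay, the detectable difference in the second window is 0.427 × √(1 − 0.003) = 0.426 SD at worst and 0.427 × √(1 − 0.169) = 0.389 SD at best. The latter equals 87/(1 − 0.169) = 105 patients per arm.

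**5. Chance imbalance.** The baseline difference between arms has SE 0.152 SD, so 1.96 × 0.152 = 0.297 SD lies at the 95% limit. It reaches the pain comparison multiplied by the slope, which is r in SD units. At r = 0.5 the shift is 0.5 × 0.297 = 0.149 SD.

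**The case against.** The strongest reply is that nothing in the plan is wrong here. Under randomisation an unadjusted two-sample comparison is unbiased and its interval is valid. Mean NRS is one of twelve secondary items, (a) to (l), and the primary outcome is not touched. All of this stands.

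The size of the gain is also uncertain. Doses are keyed to the pain score, with rescue and step-up provisions, and section B3.A itself calls the disease rapidly evolving. Both could weaken the link between starting and later pain. This stands too, and is why the windows are shown separately.

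A reader might infer four stronger things that the documents do not support:

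- *Simple randomisation lets an imbalance in starting pain bias the result.* An imbalance enters scaled by the regression slope, and the unadjusted standard error already allows for it. It is the same precision loss, not a second harm.
- *Pain at entry varies widely.* The documents give no distribution of entry pain. Spread is plausible from the recruitment route, but it is an assumption.
- *The 4-hourly data are wasted.* Averaging the scores already uses much of that information. Only the baseline covariate is missing.
- *The gain is the same in both windows.* That holds only if correlation does not fade with time.

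**Conclusion.** The point holds as an inexpensive gain in efficiency. The plan names only unadjusted tests for mean NRS, while a suitable baseline score should already be in the chart. The trial remains valid without the change.

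The gain rests on an assumed correlation. Across r = 0.3 to 0.7 it runs from modest (9% of variance) to substantial (49%). The case is strongest for the first 24 hours, at 21% to 60% under the decaying patterns tried. For the second 24 hours those patterns give only 0.3% to 17%. No figure was worked out for the whole-stay mean.

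The undefined start of the first 24 hours matters as well. If that window opens at admission, the last score before randomisation falls inside the outcome that it is meant to adjust, so the window must be anchored before the covariate can be used.

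**What to change.** 1. **B3.A, secondary outcome (b):** start the first and second 24-hour windows at randomisation, and count the whole-stay mean from randomisation, so that the baseline score is not part of the outcome.
2. **B3.A, NRS paragraph:** define baseline as the last NRS charted before randomisation. Use a score taken at consent, before the arm is disclosed, only if none is charted.
3. **B3.B.b:** analyse mean NRS for 0–24 h, 24–48 h and the whole stay by linear regression on arm with baseline NRS as covariate. Report the adjusted difference with its 95% CI.

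Make these changes before outcome data are seen, so that the choice to adjust cannot look selective. The cost is one extra data item per patient and slightly more analysis work. No extra patients are needed, and no dose or clinical rule changes.
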